Young-Healthy Subjects:

- female between the age of 18 to 39 years
- no joint or muscle pain in the hand or wrist

Exclusion Criteria:

All Groups:

- Pregnant women; minors (under age 18); mentally disabled; any persons incarcerated, on parole, on probation, or awaiting trial
- Individuals with concomitant musculoskeletal pathologies (other than osteoarthritis) in the hand or wrist, including distal radius fracture, contracture, trigger finger, and carpal tunnel
- Individuals with history of uncontrolled diabetes, rheumatoid arthritis, muscular dysfunction, or neurological disease

Recruitment:

The CMC OA subjects, age-matched control subjects, and young-healthy control subjects will be recruited, as described below:

CMC OA Subject Recruitment: Subjects with CMC OA will be recruited directly from the hand clinics at the UF Orthopaedics Sports Medicine Institute (OSMI). Specifically, a clinical member of the study team affiliated with the Department of Orthopaedics (e.g., [name]) will identify individuals who meet the inclusion criteria. These individuals will be asked at the end of their clinic visit if they are interested in learning more about the research study and potentially participating. At this time, the potential participant's contact information (name, e-mail, phone number) and preferred contact method (phone or e-mail) will be recorded. A member of the IRB-approved study team will then reach out to the potential participant by phone or e-mail to discuss the study and answer any questions. If the potential participant expresses interest, he or she will be e-mailed a copy of the informed consent document to review and discuss with their friends and/or family. The study sessions will also be scheduled at this time. Subjects will be consented in-person at the time of their first study session.

Age-Matched Control Subjects and Young-Healthy Subjects: Age-matched control subjects and young-healthy subjects will be recruited using the mechanisms listed below. It should be noted that individuals with CMC OA may also contact the study team via these mechanisms. However, the study team anticipates that these mechanisms will more readily identify age-matched control subjects:

- 1) Recruitment Flyer – An IRB-approved recruitment flyer will be posted around the University of Florida's campus and the Gainesville community in approved advertising

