If a potential participant answers "yes" to question (a) – (b) and "no" to questions (c) – (f), then we will ask the following follow-up question: "What kind of arthritis have you been diagnosed with in your hand or wrist?" If the answer is thumb OA, we will proceed with scheduling a study visit as an CMC OA subject.

Otherwise, the potential participant will be informed that he or she is ineligible to participate.

To facilitate continued communication and follow-up, we will ask the potential participant what his or her preferred method of contact is and will record his or her name, phone number, and e-mail address during these initial conversations. We will use the e-mail address to provide the potential participant with an electronic copy of the informed consent form to review prior to his or her first visit. This copy of the informed consent form will be provided to the subject at least 24 hours prior to their scheduled participation. All research subjects will be consented in-person at the time of their first study session.

Enrollment & Informed Consent:

Prior to experimental data collection, each participant will be given the opportunity to review the informed consent form and study procedures in-person with a member of the study team. This discussion will include information on study purpose and procedures, benefits and risks, who to contact (study team, IRB, etc.), that participation is voluntary and participants can withdraw at any time, HIPAA and confidentiality, as well as cost and compensation. The participant will be given the opportunity to ask questions. After all questions have been answered, the participant will sign the informed consent form, documenting that they provide consent to participate as well as authorization to access their private health information as outlined on the informed consent form.

Research Approach:

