Together, these assessments will provide insights into each subject's clinical pain experience. Specifically, the GCPS yields a "Characteristic Pain Intensity" score and an overall "Disability" score providing insight into global pain severity and pain-related interference over the past 6 months. The comprehensive pain history provides an index measure of important pain domains associated with biological aging and functioning. These domains are frequency, intensity, time (duration) and total pain sites. The AUSCAN assesses disease-related pain and is specifically designed for hand OA. The PROMIS Anxiety and Depression short forms, CES-D, and BDI screen for symptoms of mood disturbance and has been extensively validated in chronic pain populations such as OA. The MoCA evaluates different types of cognitive abilities. The CSQ-R uses a pool of items that reflect coping strategies frequently reported by patients and proven to be important in the management of pain. The LOT-R measures how optimistic or pessimistic people feel about the future which has been shown to correlate with people's health, work performance, and educational attainment. The PANAS will report how individuals generally feel with positive affect reflecting enthusiasm and negative affect reflecting distress. Subject's response to questions regarding risk of suicide will be reviewed immediately after the study. If a subject or potential subject indicates suicidal thoughts or wishes, the principal investigator of the study, [name], and a representative the UF Psychology Clinic, [name] (or their appropriate designees), will be informed. In the unexpected event that [name], nor their designees are available, the Alachua County Crisis Center will be contacted. The clinical pain metrics will be primary outcome variables of the study. The psychological measures will be used as possible covariates and support future studies that more comprehensively include

psychological measures. Subjects will be given ample time to complete all questionnaires and provided with the opportunity to ask questions about any and all measures. The questionnaires can be completed by the subject in any session (Session I or Session II) as needed.

Functional Outcome Measures.

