Clinical Pain, Psychological, and Function Measures: The questionnaires and functional tasks proposed in this study are considered minimal risk. Some individuals may feel unconformable with some questions. Notably, the PROMIS short for screening for anxiety and depression may indicate that a research subject is anxious or depressed. These forms will be scored prior to the completion of the session. An elevated score, meaning an individual is anxious and/or depressed will be handled by contacting one of the clinical co-Investigators ([name] or [name]) and obtaining the appropriate referrals.

Radiation Exposure. There is an extremely small chance that research subjects will be more susceptible to developing cancer because of increased exposure to radiation experienced during the radiographs required for this study. However, the risk due to exposing the hand, a distal segment that is not close to vital organs, to the radiation from an x-ray is extremely low. The Food and Drug Administration (FDA) Guidelines for Research Subjects sets an estimated dose equivalent (EDE) limit of 3 rem for a single session and no more than 5 rem annually. The total EDE associated with participation in this study is estimated to be less than 2 mrem (note the difference in units). This is less than 1 percent of the amount of background radiation that the average person in the United States receives each year (annual background radiation estimated to be 0.36 rem).

Additional Protections Against Risk:

The study design provides several measures to minimize the potential risks to subjects:

Minimizing Risks to Privacy by Protecting Confidentiality: The collected PHI includes, age and biological sex. This information will only be identifiable by a subject specific code. A document linking the subject specific code to the name of the subject will be stored securely in a locked cabinet within [name] laboratory and/or electronically on a password-protected

server in the University of Florida. Only IRB approved research personnel will have access to identifiable research data.

Minimizing Risks by Using Qualified Study Personnel

We will also protect subjects by having appropriately trained personnel perform/oversee the necessary procedures. The radiographs will be acquired at UF Health in a manner identical to that used on patients, such that privacy and safety will be ensured. Trained and qualified technicians employed by the University of Florida will obtain all scans.

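### Review of suicide-risk answers is timed after the study session, so it is not secured before the participant leaves

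*Protocol*

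**What the plan says.** Two rules in the protocol govern how soon sensitive questionnaire answers are looked at.

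- **Suicide-risk answers** (section 6, Session II, Clinical Pain & Psychological Measure). The participant's "response to questions regarding risk of suicide will be reviewed immediately after the study". The escalation rule follows: "If a subject or potential subject indicates suicidal thoughts or wishes", the principal investigator and a representative of the university psychology clinic, or their designees, are informed. The county crisis center is contacted if none of them is available.
- **PROMIS anxiety and depression forms** (section 7, Clinical Pain, Psychological, and Function Measures). "These forms will be scored prior to the completion of the session". The follow-up is also fixed: "An elevated score, meaning an individual is anxious and/or depressed will be handled by contacting one of the clinical co-Investigators", with referral as appropriate.

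Three other provisions bear on the point.

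- The place of completion is flexible: "The questionnaires can be completed by the subject in any session (Session I or Session II) as needed".
- Under Research Approach in section 6, the three sessions may run on one day or as separate visits, in any order.
- Contact details are taken before the first visit. For clinic patients, "contact information (name, e-mail, phone number) and preferred contact method (phone or e-mail) will be recorded". For people who approach the study team themselves, the team "will record his or her name, phone number, and e-mail address during these initial conversations".

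**The concern.** An answer about suicide is the most urgent item that any of these questionnaires can produce. Yet the protocol sets a firmer time for a general mood score than for that answer. The PROMIS forms must be scored while the session is still running. The suicide-risk answers need only be read afterwards, and no sentence requires that the participant still be on site.

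What is at stake is participant safety, not inference. Someone who indicates suicidal thoughts only on paper could walk out before a staff member reads the form. The escalation route starts with someone knowing of the disclosure. For a written-only disclosure, nobody knows until the form is read. Reaching the person after departure is possible, but it is slower and harder than speaking to her in the room.

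**Working it through.** No arithmetic applies. The question is one of timing, so the check is to set the provisions side by side.

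1. **When is each item looked at?** The PROMIS forms are scored before the session is complete. The suicide-risk answers are reviewed immediately after the study. Measured against the end of the session, the first rule falls before it. The second, on its most natural reading, falls just after it.

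2. **What does the word study mean here?** The sentence does not say session or visit. The word immediately and the urgent escalation that follows both point to the session just finished. The rest of this check uses that milder reading.

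3. **Does any sentence hold the participant until the review is done?** None was found in the questionnaire text of section 6, in the description of the sessions under Research Approach, or in the protections listed in section 7. A review made as the session closes, with the participant present, would satisfy the sentence. So would a review made a few minutes after she has gone. The sentence permits both, and that is the defect.

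4. **Does the PROMIS rule close the gap?** Not reliably. Section 6 names the PROMIS forms, the CES-D and the BDI as screens for mood disturbance, but the in-session rule in section 7 names only PROMIS. The protocol does not say which questionnaire carries the suicide-risk questions. An elevated PROMIS score may prompt contact with a clinical co-investigator, but it is not a reading of the suicide-risk answer.

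5. **Do the other safeguards close it?** They narrow it.
   - The escalation trigger is any indication by a subject or potential subject, so a spoken statement would start it at once.
   - Recorded telephone and e-mail details mean that a participant who has left can be reached.
   - Responders and a back-up are designated.

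   None of these ensures that a written answer is read before departure.

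6. **What remains?** Three conditions have to coincide: the disclosure is made only in writing, the participant leaves before the review, and no elevated PROMIS score has already led to contact. The protocol gives no rate for any of these and no length for the interval. All 60 planned participants come under the rule, but that is the number reviewed, not the number at risk.

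**The case against.** The best reply is that the word immediately already does the work. It is a firm requirement, it can be met with the participant still in the room, and nothing says she is released first. The two timing rules concern different items and can both be followed, so they do not contradict each other. The protocol also layers its protections: prompt review, responders with designees, a crisis center, in-session PROMIS scoring and contact details. On this view, adding a few words about departure is a wording clarification.

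Much of that stands, and it is why the point is rated minor. It does not remove the point. A safety instruction that is met equally well by review before or after departure leaves the choice to whoever runs the session. The PROMIS rule shows that the team regards in-session scoring as workable.

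A reader might infer more than the protocol supports, in three ways.

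- **That review could wait until after the last visit.** Sessions may be spread over separate visits, and the bare wording would allow this. It fits poorly with the word immediately and with the escalation that follows, so nothing here rests on it.
- **That staff could act only by telephone or e-mail once the participant has left.** The protocol does not say so. It brings in a psychology clinic representative and a crisis center without limiting how they respond, and a participant with another session that day may still be nearby.
- **That the plan for suicidal disclosure is missing.** It is not. The route is set out, and only the moment at which a written answer sets it off is loose.

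**Conclusion.** The point holds as a minor one. The protocol fixes the time of the suicide-risk review loosely. Review before the participant leaves is allowed but not required, while a less urgent mood score must be ready before the session is complete.

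The exposure is narrow: a participant whose only disclosure is written and who leaves before it is read. The consequence is a delayed and more difficult response. It is not an absent one, because the escalation route and the contact details remain available.

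This rests on reading the phrase as right after the session. It does not depend on which questionnaire holds the suicide-risk questions. The size cannot be put in figures, since the protocol states neither the expected number of such disclosures nor the interval to review, which may be only minutes. Sample size, endpoints and analysis are unaffected.

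**What to change.** In section 6, Clinical Pain & Psychological Measure, replace the timing phrase. The sentence should require that answers on suicide risk, on whichever questionnaire they appear, are reviewed before the participant leaves the session (I or II) in which they are given. Naming the session matters because the questionnaires may be completed in either one. Leave the escalation route and the PROMIS rule in section 7 as they are.

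The cost is one amended sentence and, for some participants, a wait of a few minutes at the end of the session. The review is already planned, so only its timing moves.

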1. PROJECT TITLE

Carpometacarpal Osteoarthritis: Towards Identification of Biomechanical, Neuromuscular, and Somatosensory Mechanisms

2. INVESTIGATOR(S):

Principal Investigator: [name].
Assistant Professor
J. Crayton Pruitt Family Dept. of Biomedical Engineering

Co-Investigators: [name].
Professor and Chief Hand & Upper Extremity
Department of Orthopaedics

[name], M.S.P.H, Ph.D.
Assistant Professor
Dept. Aging & Geriatric Research

Other Study Personnel: [name]
Ph.D. Graduate Student
J. Crayton Pruitt Family Dept. of Biomedical Engineering

3. ABSTRACT:

This study examines carpometacarpal osteoarthritis (CMC OA). We specifically aim to elucidate the biomechanical, neuromuscular, and somatosensory mechanisms that contribute to CMC OA symptoms by using orthopaedic biomechanics and quantitative pain testing. Completion of this study will provide a comprehensive dataset describing how movement strategies (muscle activity and joint posture) as well as experimental and clinical pain differ between individuals with CMC OA and age-matched controls.

4. BACKGROUND:

Over 13 million Americans suffer from symptomatic hand OA.⁶ Involvement of the CMC joint at the base of the thumb (Fig. 1) is particularly disabling. Individuals with CMC OA can lose up to 50% of hand function.² Current conservative and surgical treatments do not provide the pain relief, strength, and mobility needed to restore both fine and gross motor function.⁷ Conservative treatments, such as physical therapy, orthoses, anti-inflammatory drugs, and local steroid injection are effective for short-term pain relief, but offer minimal functional improvements.^{8, 9} Surgically treating CMC OA provides long-term pain relief, but has the unintended consequence of limiting mobility and strength.⁷ Unlike OA at the hip or knee, total joint arthroplasty is not standard of care for CMC OA.¹⁰ Instead, CMC OA is surgically treated with ligament reconstruction and/or bone excision.⁷ This translates into over eight different surgical options.³ No one surgery has proven superior and there is no consensus on how to choose between the surgical options.³

[figure not shown]

Figure 1. (A) The CMC joint connects the first metacarpal and trapezium. (B) X-ray of mild CMC OA from Ladd et al.¹

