is expected to be improved understanding of how biomechanical, neuromuscular, and somatosensory mechanisms influence symptom severity in adults with CMC OA. This contribution is *significant* as it directly addresses the primary barrier preventing the design of new, optimal treatments: the mechanisms that influence the severity of CMC OA have not been fully identified, and therefore cannot be clinically targeted.

[figure not shown]

Figure 2. To alleviate CMC OA symptoms, we must understand multiple mechanisms.

5. SPECIFIC AIMS:

Individuals with symptomatic thumb carpometacarpal osteoarthritis (**CMC OA**) can lose up to 50% of hand function.² Surgical treatments aim to restore function and reduce pain by eliminating instability at the CMC joint. However, there are eight different surgeries commonly used, and no consensus on how to optimally choose between them.³ Treatment is also challenging because the presentation of symptoms is highly variable.⁴ For example, 33% of postmenopausal women have radiographic evidence of thumb CMC OA,⁵ yet only 5% of all women visit the doctor with symptoms.⁴ Some individuals may employ unique coping mechanisms that prevent development of pain and functional loss, while others may simply use over-the-counter medications to avoid the doctor. Regardless, very little is known about how an individual's symptoms relate to the underlying osteoarthritic disease. My *long-term goal* is to design effective, targeted treatments for individuals with CMC OA. As a critical step toward this goal, the *objective of this proposal* is to elucidate the biomechanical, neuromuscular, and somatosensory mechanisms that occur during aging and contribute to the symptomology of CMC OA. This objective will be accomplished through two aims:

Aim 1. Evaluate how muscle activity, joint kinematics, and CMC joint stability change in the presence of movement-evoked pain. Electromyography (EMG), joint kinematics, CMC joint stability, and movement-evoked pain during three functional tasks will be quantified in adults with end-stage CMC OA, age-matched controls, and young-healthy individuals. We *hypothesize* that greater levels of reported pain during task completion will be associated with increased muscle activity, larger joint angles, and decreased joint stability. Completion of this aim will quantitatively characterize biomechanical and neuromuscular mechanisms that influence CMC OA symptomology.

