Aim 2. Quantify the relationship between function, pain symptomology, and disease severity. Hand function, clinical and experimental pain, and disease severity will be measured in adults with end-stage CMC OA, age-matched controls, and young-healthy individuals. We *hypothesize* individuals with CMC OA will demonstrate greater functional deficits and higher experimental pain sensitivity than age-matched controls and young-healthy individuals. Additionally, in individuals with CMC OA, we hypothesize that functional loss will be associated with higher clinical pain, but not necessarily higher disease severity. Completion of this aim will comprehensively and quantitatively characterize the multi-faceted symptomology of CMC OA and provide insights into the somatosensory mechanisms affecting this disease.

6. RESEARCH PLAN:

Sample Size & Justification: A total of 60 subjects will complete the proposed research study: 20 individuals with end-stage CMC OA, 20 age-matched controls, and 20 young-healthy individuals. These subjects will represent the racial and ethnic diversity of the state of Florida. Vulnerable populations including pregnant women and prisoners will be excluded. All subjects will be between the ages of 18 to 90. Specifically, the end-stage CMC OA cohort and age-matched controls will be between the ages of 40 to 90 as CMC OA is most prevalent in older adults. While the young-healthy cohort will be between the ages of 18-39. A power analysis ($\alpha = 0.05$, $1-\beta = 0.80$) to detect 20% differences in pinch strength between groups required 15 individuals per cohort. Due to including a young-healthy cohort and to prevent erroneous inferences to occurs after multiple comparisons, 20 individuals per cohort will be recruited. Note, pinch strength was the only relevant variable for which standard deviations could be consistently estimated from the literature.^{23, 36} Thus, an important outcome of this pilot project will be the data necessary to robustly estimate sample sizes for future studies. For reference, prior studies indicate that individuals with early-stage CMC OA have 20-30% less pinch strength than controls.^{23, 36}

A summary of inclusion and exclusion criteria are provided below:

Inclusion Criteria:

CMC OA Subjects:

- female between the age of 40 to 90 years
- end-stage CMC OA diagnosed by a board-certified clinician

Age-Matched Control:

- female between the age of 40 to 90 years
- no joint or muscle pain in the hand or wrist

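### The phone screen refuses self-referred CMC OA subjects who have hand pain, although the eligibility criteria contain no such rule, so pain level becomes tied to recruitment route

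*Protocol*

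**What the plan says.** **Eligibility (Protocol section 6, Inclusion and Exclusion Criteria).** A CMC OA subject must be a woman aged 40 to 90 with "end-stage CMC OA diagnosed by a board-certified clinician". Neither this list nor the exclusions for all groups mention hand pain for her. Both control groups, by contrast, must have "no joint or muscle pain in the hand or wrist".

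**Recruitment (section 6).** CMC OA subjects are identified in the hand clinics against the inclusion criteria: "These individuals will be asked at the end of their clinic visit". The same section notes that women with CMC OA may also respond to the flyer, website or word of mouth, but expects these routes to find controls more readily.

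**Phone screen (section 6, Initial Contact with Study Team).** Question (c) asks about current muscle or joint pain in the hand or wrist. Question (d) asks about such pain needing medical attention or physical therapy in the last 6 months. A caller who reports diagnosed arthritis is scheduled as a CMC OA subject only if she answers no to (c) through (f) and her arthritis is thumb OA. Every pattern outside the control branch and this one leads to a statement of ineligibility.

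**Use of pain.** Under Clinical Pain & Psychological Measure: "The clinical pain metrics will be primary outcome variables of the study". Aim 1 expects that "greater levels of reported pain during task completion will be associated with increased muscle activity, larger joint angles, and decreased joint stability". Aim 2 expects, within CMC OA, that "functional loss will be associated with higher clinical pain, but not necessarily higher disease severity".

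**The concern.** The written criteria and the operating script define two different CMC OA populations. The clinic route can admit women with any level of hand pain. The phone route admits only women with no current hand pain and none recently treated.

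Two things follow. First, a team that follows the script turns away women who meet the written criteria, and no later analysis can recover them. Second, low pain becomes a marker of having phoned in. Women who answer a flyer may differ from hand-clinic patients in age, radiographic severity or function for reasons unrelated to pain. Pooled in one correlation, such a difference would appear as an association between pain and function, which is the clinical-pain hypothesis of Aim 2.

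**Working it through.** **Setting the passages side by side (one woman, two routes)**

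Take a woman of 60 with clinician-diagnosed end-stage CMC OA, a currently painful thumb and no exclusion.
- Inclusion and Exclusion Criteria: eligible.
- Hand clinic: identified against those criteria and invited.
- Phone: yes to (a) and (b), yes to (c), and yes to (d) if the pain was treated in the last 6 months. She is told that she is ineligible.

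The conflict needs no arithmetic. Its possible effect on the Aim 2 association does. The protocol's only computed figure, 15 per cohort, concerns pinch strength and has no bearing here.

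**Inputs**
- From the protocol: 20 CMC OA subjects; alpha 0.05, taken as two-sided because the side is not stated.
- Assumed, because the protocol gives no figures: k = 2 or 5 of the 20 enter by phone; functional loss is lower by d = 0.5 or 1.0 SD among them; there is no pain-function association within either route.
- Pain model (assumed): latent pain is standard normal. Phone entrants come from the lowest 20% and score 0. Clinic subjects come from the rest and score their distance above the cut.

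**Hand check of the induced correlation**

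The cut is a = -0.842, and λ = 0.280/0.8 = 0.350. Clinic pain then has mean μ = 0.350 + 0.842 = 1.192 and variance σ² = 1 + aλ - λ² = 1 - 0.295 - 0.122 = 0.583.

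With π = k/20, the large-sample pooled correlation is

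r = π(1-π)dμ / √{[(1-π)σ² + π(1-π)μ²] × [1 + π(1-π)d²]}

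- k = 2 (π = 0.10), d = 0.5: 0.0536 / √(0.6525 × 1.0225) = 0.066
- k = 2, d = 1.0: 0.1072 / √(0.6525 × 1.09) = 0.127
- k = 5 (π = 0.25), d = 0.5: 0.1117 / √(0.7035 × 1.0469) = 0.130
- k = 5, d = 1.0: 0.2234 / √(0.7035 × 1.1875) = 0.244

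**Simulation at n = 20** (200,000 draws per cell, Pearson t-test)

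| Self-referred of 20 | Route difference d | Mean r | False-positive rate |
|---|---|---|---|
| 2 | 0.5 SD | 0.07 | 5.8% |
| 2 | 1.0 SD | 0.13 | 7.9% |
| 5 | 0.5 SD | 0.14 | 8.6% |
| 5 | 1.0 SD | 0.26 | 18.5% |

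With d = 0 the rate is 5.0-5.1%. The simulated mean r agrees with the hand check, slightly higher because of the small sample.

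**Does the phone route cost power?**

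Same pain model, no route difference, and an assumed true correlation of 0.59. That is about what 20 subjects detect with 80% power: tanh((1.960 + 0.842)/√17) = 0.591.

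| Self-referred of 20 | Clinic subjects all painful | Clinic subjects unselected |
|---|---|---|
| 0 | 61% | 79% |
| 5 | 82% | 83% |
| 10 | 83% | 78% |

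Power is not materially reduced. If clinic patients are all painful, adding pain-free women widens the range of pain and raises it.

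**The case against.** **Few women may be affected.** The protocol recruits CMC OA subjects from the hand clinics and expects the other routes to yield mainly controls. With 2 of 20 self-referred, the false-positive rate is only 6-8%, and even that needs an assumed route difference in function. This stands and limits the size of the point. It does not remove the contradiction.

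**Scoring phone entrants as zero is harsh.** The Graded Chronic Pain Scale covers global pain over 6 months. Question (c) concerns pain at the time of the call, and question (d) only pain that needed care. A woman who passes can still score above zero, and a task can still provoke pain in Aim 1. This stands too: the figures fit current hand pain best and overstate the effect on broader measures.

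**Low-symptom women are relevant.** The protocol is motivated by the gap between radiographic disease and symptoms, so admitting them is sensible. Agreed. The difficulty is that one route admits only them.

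**Stronger readings that the protocol does not support.**
- A reader might infer that the primary analysis is a comparison of clinical pain between CMC OA and pain-free controls, with the result built in by eligibility. No such test is planned. Aim 2's between-group hypothesis is that "individuals with CMC OA will demonstrate greater functional deficits and higher experimental pain sensitivity than age-matched controls and young-healthy individuals", which leaves clinical pain out, and the abstract only promises data describing how "experimental and clinical pain differ between individuals with CMC OA and age-matched controls".
- A reader might infer that phone entrants add nothing to the correlation, so that the sample shrinks to the clinic subjects. The power check shows otherwise: zeros are data.
- A reader might infer from the radiograph section, which mentions lack of disability, that controls are selected on function. That is loose explanatory text, and the eligibility lists contain no disability criterion.

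**Conclusion.** The contradiction is certain from the text: the phone screen imposes two pain conditions on self-referred CMC OA subjects that the eligibility criteria do not contain and the clinic route does not apply. The harm is wrongful exclusion of eligible symptomatic women, together with confounding of pain level by recruitment route.

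The statistical size is modest and conditional. It is about 6-8% false positives with 2 of 20 self-referred and 9-19% with 5, against a nominal 5%. This rests on an assumed 0.5-1.0 SD route difference in function, phone entrants scoring zero, and no true association. If function does not differ by route, there is no inflation and no material loss of power. The matter should be corrected. It does not invalidate the design.

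**What to change.** 1. Reconcile Initial Contact with Study Team with the CMC OA Inclusion Criteria on questions (c) and (d), so that one eligibility rule applies to CMC OA subjects whichever way they reach the study. Which rule that is remains for the investigators to decide.
2. Record the recruitment route (clinic or self-referred) of each CMC OA subject. If anyone was enrolled under the differing rules, show the pain-function association by route as well as pooled. The Data Storage section limits what is documented with the data to age, sex and a subject code, so it needs a matching update.
3. Optional: add a sentence under Clinical Pain & Psychological Measure saying that, because controls are enrolled without hand or wrist pain, CMC OA versus control differences on hand-specific pain scores such as the AUSCAN are descriptive.

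The cost is an IRB amendment to protocol and phone-script wording and one extra recorded variable, with no added subjects or tests. It is best done before further enrolment, since women already turned away cannot be recovered in the analysis.
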